# 6.4 Reporting Unanticipated Adverse Device Effects

A sponsor who conducts an evaluation of an UADE under §812.46(b) shall report the results of such evaluation to FDA and to all reviewing IRB's and participating investigators within 10 business days after the sponsor first receives notice of the UADE. Thereafter the sponsor shall submit such additional reports concerning the effect as FDA requests. The site will complete an UADE event eCRF form within 24 hours of the Investigator being notified of the UADE. The report will be scanned and emailed to [contact] and then forwarded for Alcresta Chief Medical Officer review.

Title: Absorption and Safety with Sustained Use of Relizorb™ Evaluation (Assure) Study in Patients With Cystic Fibrosis Receiving Enteral Feeding

In addition, any event that results in a subject's withdrawal from the study must be reported directly to the Alcresta Chief Medical Officer as soon as possible but no later than 24 hours.

# 7.0 STATISTICAL PROCEDURES AND DATA ANALYSIS

### 7.1 General Considerations

Data collected in this study will be presented using summary tables, subject data listings and figures. Summary tables will present data by subject and, if applicable, by study visit. Continuous variables will be summarized using descriptive statistics, specifically the mean, median, standard deviation, minimum and maximum values. Categorical variables will be summarized by frequencies and percentages. Figures may be used to support the presentation of certain data.

All available data will be included in data listings. No imputation of values for missing data will be performed, unless otherwise specified. The relevance of missing sample data will be assessed. In the case of subject withdrawal from the study, data collected at the Day 30 and Day 60 time point will be employed in the analysis of that time point but those values will not be carried forward. Data that are potentially spurious or erroneous will be examined according to data management standard operating procedures.

Qualitative or descriptive data will be analyzed to evaluate against safety and tolerability endpoints. The potential influence of other covariates such as age, gender, ethnicity, height and weight will be examined.

# 7.2 Determination of Sample Size

The proposed study with 30 complete and evaluable subjects would have 80% power to detect a minimum effect size of 0.53. Based on literature reviews using 1.5% as the maximum standard deviation expected when measuring DHA levels, the study should be able to detect an absolute increase of at least 0.8% from the baseline DHA value after 90 days of Relizorb use (i.e., a change from 3.0% at baseline to 3.8% after 90 administration days or a 27% relative increase). This sample size will be adequate to detect the desired 30% relative increase in DHA levels.

# 7.2.1 Stopping Rules

Relizorb is a low risk medical device, and the patient population under study is at relatively low risk for a severe adverse experience. Therefore, there are no prospective stopping rules for this study.

Title: Absorption and Safety with Sustained Use of Relizorb™ Evaluation (Assure) Study in Patients With Cystic Fibrosis Receiving Enteral Feeding

The Alcresta Chief Medical Officer will review all UADEs as they occur. In addition, every 30 days all UADEs will be reviewed in aggregate starting from the first subject enrolled until the last subject has completed the study. Based on this planned surveillance, the Alcresta Chief Medical Officer will convene a teleconference with the chair of the Data Safety Monitoring Board (DSMB) as soon as possible if any of the following occur:

- Death of any subject in the study, regardless of causality,
- Two occurrences of the same UADE where causality has been assigned to Relizorb use by the site PI, or more than three occurrences of the same UADE regardless of causality,
- A trend emerges in the occurrence of similar UADEs.

If either the Alcresta Chief Medical Officer or the chair of the DSMB has a concern regarding the safety of study subjects, the Chief Medical Officer will convene a teleconference with the DSMB and the site PIs as soon as possible to discuss the potential safety issue. Possible outcomes of the teleconference include:

- Continuation of the study with no change in study conduct if it is determined that there is no safety issue,
- Placing the study on clinical hold until the study protocol can be modified to mitigate the safety issue,
- Termination of the study.

#### 7.3 Randomization

Randomization will not be used in this open label study.

## 7.4 Populations for Analysis

## 7.4.1 Per Protocol Population

The per protocol population consists of all subjects who met the inclusion criteria, used Relizorb as stated in the protocol and IFU through at least Visit 3 (Day 30) and has not been the subject of any major protocol deviation.

## 7.4.2 Safety Population

The safety population includes all subjects who received at least one Relizorb exposure. For subjects who withdraw from the study, every effort will be made to retrieve all relevant safety information.

Title: Absorption and Safety with Sustained Use of Relizorb™ Evaluation (Assure) Study in Patients With Cystic Fibrosis Receiving Enteral Feeding

## 7.5 Procedures for Handling Missing, Unused and Spurious Data

All available safety and tolerability data will be presented in data listings and tabulations. No data imputation will be applied for missing values. The relevance of missing sample data will be assessed. Data that are potentially spurious or erroneous will be examined according to standard data management operating procedures.

In the case of subject withdrawal from the study, data collected at the Day 30 and Day 60 time point will be employed in the analysis of that time point but those values will not be carried forward.

## 7.6 Demographics and Baseline Characteristics

Demographic and baseline characteristics will be summarized and presented overall. Demographic data to be evaluated will include age, sex, ethnicity, height, weight and BMI. Demographic data will be presented in a by-subject listing. Age will be calculated from date of birth to date informed consent was obtained.

## 7.7 Safety Analysis

Safety will be assessed based on the incidence, severity, and type of AE and UADE, clinically significant changes or abnormalities in the subject's clinical laboratory results and vital signs. For clinical laboratory tests, descriptive summaries of actual values and changes from the baseline will be presented. Descriptive statistics will be provided for vital sign measurements collected during clinic visits.

AE and UADEs will be recorded throughout the study and listed in summary tables in terms of severity and causal relationship to Relizorb use. Relationship assessments that indicate the AE is "Not Related" is an event related to etiology, rather than from Relizorb use. "Related" is defined as an association between the AE or UADE and Relizorb use. Other selections include "Possibly Related" and "Probably Related".

The gastrointestinal symptoms recorded in the 7 day gastrointestinal symptom diary during the run in period will be compared with the symptoms recorded three separate times during the treatment period. Each symptom will be categorized as a) occurring or not occurring b) rated as a 1,2, or 3 in severity, and lasting in duration for less than 15 minutes, 15 to 30 minutes, 31 to 60 minutes, or greater than 60 minutes.

For the comparison between symptoms recorded during the run in period and the treatment period, the following analyses will be performed:

Number of days where any symptom occurred;

Title: Absorption and Safety with Sustained Use of Relizorb™ Evaluation (Assure) Study in Patients With Cystic Fibrosis Receiving Enteral Feeding

- Number of days each symptom occurred;
- For each symptom, number of days when the severity was a 1, 2, and 3
- For each symptom, number of days when the symptoms lasted in duration for less than 15 minutes, 15 to 30 minutes, 31 to 60 minutes, or greater than 60 minutes.

Comparison of these values during the run in and treatment periods will be performed using analysis of variance (ANOVA).

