### Safety

- Frequency and severity of adverse events and unanticipated adverse device effects (UADEs)
- Evaluation of clinical and laboratory findings
- · Concomitant medication assessment
- Frequency and severity of gastrointestinal signs and symptoms (abdominal pain, vomiting, loss of appetite, bloating, flatulence and steatorrhea)

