# 6.2.2 Anticipated Adverse Events in Subjects

Due to the GI complications inherent in CF patients, the identified risks are upper abdominal pain, bloating, constipation, diarrhea, flatulence, heartburn, indigestion, nausea, steatorrhea (fatty stool), vomiting, weight decrease and headache.

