9.1 Adverse Events

All AEs will be coded using the Medical Dictionary for Regulatory Activities (MedDRA Version 18.0 or most recent version).

AEs will be summarized by MedDRA system organ class and preferred term. Separate columns will be included in the AE summary table for AEs starting under the treatment by Standard of Care, and starting during RELiZORB treatment.

For all AEs, the event will be summarized under the treatment (Standard of Care, RELiZORB) the event started in and in the total column. The AE is assigned to the standard of care or RELiZORB based on the start date of the adverse event.

- If the start date of the event is before the first administration of RELiZORB, the event will be summarized under Standard of Care.
- If the start date of the event is on or after the first administration of RELiZORB, the event will be summarized under RELiZORB.
- If the start and end date of the event are both missing, the event will be summarized under both SOC and RELiZORB.

In a general overview of AEs, events will be summarized by treatment for the following items:

- All AEs
- Serious Adverse Events (SAEs)
- AEs by relationship
- AEs leading to discontinuation of enteral feeding
- AEs by maximum severity
- UADEs
- UADEs by relationship
- UADEs leading to discontinuation of enteral feeding
- UADEs by maximum severity

Missing and partially missing AE start and/or stop dates will be imputed, for the purpose of statistical analysis, according to the specifications described in Section 6.2.

Summaries of incidence rates (frequencies and percentages) of individual AEs by MedDRA System Organ Class and preferred term will be prepared. UADEs and SAEs will not be included in summaries of AEs, but will be summarized separately. Each subject will be counted only once within each level of summary (system organ class and preferred term).

Adverse events that lead to discontinuation of enteral feeding will be summarized and listed separately.

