14.2.1.7	ITT	Changes over Time in Serum Protein Concentrations (Total Protein, Prealbumin, Albumin, and Transferrin)	16.2.5.6.1
14.2.1.8	ITT	Changes over Time in Urinary Leukotriene E4	16.2.5.7.1
14.2.1.9a	ITT	Changes over Time in Plasma Concentrations of Fat Soluble Vitamins (A, D, and E)	16.2.5.5.1
14.2.1.9b	ITT	Changes over Time in Plasma Concentrations of Fat Soluble Vitamins (A, D, and E) by Age Subgroup	16.2.5.5.1
14.2.1.10	ITT	Weight and Body Mass Index (BMI) Z-scores by Age Subgroup and Comparison to Historic Z-score	16.2.5.10.1
14.2.1.11	ITT	Changes over Time in Weight Gain Velocity (g/kg/90 days) Compared to Historical by Age Subgroup	16.2.5.9.1
14.3.1.1	Safety	Summary of Adverse Events	16.2.6.1, 16.2.6.2, 16.2.6.3, 16.2.6.5
14.3.1.2	Safety	Adverse Events by System Organ Class and Preferred Term	16.2.6.1
14.3.2.1	Safety	Unanticipated Adverse Device Effects by System Organ Class and Preferred Term	16.2.6.3
14.3.2.2	Safety	Unanticipated Adverse Device Effects by System Organ Class, Preferred Term, and Relationship	16.2.6.3
14.3.2.3	Safety	Unanticipated Adverse Device Effects by System Organ Class, Preferred Term, and Severity	16.2.6.3

Table Number	Population	Title	Listing Reference
14.3.3.1	Safety	Gastrointestinal Symptom Diary: Frequency and Incidence – Overall and by Symptom	16.2.7.1
14.3.4.1	Safety	Summary of Clinical Chemistry Measurements: Results and Change from Baseline	16.2.8.1
14.3.4.2	Safety	Summary of Hematology Measurements: Results and Change from Baseline	16.2.8.2
14.3.4.3	Safety	Summary of Numeric Urinalysis Measurements: Results and Change from Baseline	16.2.8.3
14.3.4.4	Safety	Summary of Blood Lipids: Results and Change from Baseline	16.2.8.4
14.3.5.1	Safety	Summary of Vital Sign Measurements: Results and Change from Baseline	16.2.9.1
14.3.6.1	Safety	Concomitant Medications	16.2.3.3

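### The SAP gives AE type, severity and relationship in separate tables, so no planned table shows which GI events were severe or device-related unless they qualify as UADEs

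*Protocol*

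**What the plan says.** **Protocol.** Section 7.7 bases the safety assessment on three attributes together: "Safety will be assessed based on the incidence, severity, and type of AE and UADE". It continues: "AE and UADEs will be recorded throughout the study and listed in summary tables in terms of severity and causal relationship to Relizorb use". Section 3.2 lists as a safety endpoint "Frequency and severity of gastrointestinal signs and symptoms (abdominal pain, vomiting, loss of appetite, bloating, flatulence and steatorrhea", and Section 4.9.11 calls the diary-based frequency and severity of GI symptoms the primary safety endpoint. Section 6.2.2 names the events expected in this population: "the identified risks are upper abdominal pain, bloating, constipation, diarrhea, flatulence, heartburn, indigestion, nausea, steatorrhea (fatty stool), vomiting, weight decrease and headache". Section 6.3 restricts a UADE to a serious effect or problem associated with the device that was not previously identified in nature, severity or degree of incidence.

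**SAP.** Section 2.2.1 keeps the frequency and severity of AEs as a safety endpoint, but for GI symptoms it names incidence only. The general overview in Section 9.1 includes "AEs by relationship" and "AEs by maximum severity", by treatment period. In Section 12.1 the only by-term table for AEs is "Adverse Events by System Organ Class and Preferred Term" (14.3.1.2). The by-term tables that add an attribute are for UADEs: one for relationship (14.3.2.2) and one titled "Unanticipated Adverse Device Effects by System Organ Class, Preferred Term, and Severity" (14.3.2.3). Section 9.1 also keeps UADEs and SAEs out of the AE summaries and says they will be summarized separately, whereas Section 9.1.2 says SAEs will be listed and not summarized. Section 10 records that the diary severity and duration analyses were removed because self-reported severity is not validated.

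**The concern.** The device takes the place of enzyme use at tube feeds, so a central tolerability question is whether abdominal pain, vomiting, bloating and similar events on the device were severe, and whether investigators attributed them to it. Answering that requires type and severity, or type and relationship, in the same table. An overview row with a number of severe AEs cannot distinguish severe vomiting during feeds from a severe respiratory event unrelated to the device. A by-term incidence table shows that vomiting occurred but not how bad it was.

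The SAP provides the joint view only for UADEs, a category that may contain few events or none. Once diary severity is dropped, investigator-graded AEs are the remaining source of GI severity, and their grades are not tabulated by term.

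**Working it through.** No sample size, power or event rate enters this point, so the check is a reading of the planned table index against the event definitions.

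**Step 1: what each planned AE or UADE table carries** (SAP 12.1, with the content of 14.3.1.1 taken from SAP 9.1).

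| Table | Events | By term | Severity | Relationship |
|---|---|---|---|---|
| 14.3.1.1 | All AEs, SAEs, UADEs | No | Yes, in aggregate | Yes, in aggregate |
| 14.3.1.2 | AEs | Yes | No | No |
| 14.3.2.1 | UADEs | Yes | No | No |
| 14.3.2.2 | UADEs | Yes | No | Yes |
| 14.3.2.3 | UADEs | Yes | Yes | No |

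Of 5 tables, 2 cross term with an attribute, and both are restricted to UADEs. For AEs in general the count is 0.

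**Step 2: the anticipated events.** Protocol 6.2.2 names 12. Ten are gastrointestinal: upper abdominal pain, bloating, constipation, diarrhea, flatulence, heartburn, indigestion, nausea, steatorrhea and vomiting. The other two are weight decrease and headache, so 10 + 2 = 12.

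**Step 3: where a GI event would appear.**

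- *Non-serious, anticipated.* It adds to the aggregate severity and relationship counts in 14.3.1.1 and appears by term in 14.3.1.2 without either attribute. It cannot enter the UADE tables because it is not serious. By-term tables showing its severity or relationship: 0.
- *Serious, but anticipated in nature, severity and incidence.* It is an SAE and not a UADE. Read literally, SAP 9.1 takes it out of 14.3.1.2, and 9.1.2 leaves it to a listing. It can be counted in the overview, but by-term tables in which it appears at all: 0.
- *Serious, device-associated, and unexpected in severity or degree of incidence.* It can be a UADE and would then appear in 14.3.2.1 to 14.3.2.3.
- *Diary symptom.* Table 14.3.3.1 gives incidence and number of days. Tables showing its severity: 0.

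**Step 4: the data already exist.** Protocol 6.2.1 requires a causality assessment for every AE, the overview already uses both attributes, and SAP 9.1.1 already states the rule of counting each subject once at the strongest relationship or greatest severity within each level.

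**The case against.** A reader might infer that the SAP breaks a protocol commitment and hides the change. The documents do not support that. The sentence in protocol 7.7 does not mention system organ class or preferred term, and the overview supplies AE severity and relationship in aggregate. Since the protocol never specified a by-term AE table, SAP Section 10 had no such loss to declare. The removal of diary severity is declared there, with a reason.

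Nor do UADEs shut out GI events altogether. Protocol 6.3 is met if a serious event was not previously identified in nature, severity or incidence, so an anticipated kind of event can still qualify.

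Three further objections carry weight. The study is single-arm with about 30 to 40 subjects (SAP 3.3), and a full AE listing (16.2.6.1) is planned, so a determined reader could recover the information. GI symptoms still get incidence and days per period before and on the device, and AEs leading to discontinuation of enteral feeding are summarized separately. Finally, the table shells are not in the text available for review, so the content of 14.3.1.1 and 14.3.1.2 is read from their titles and SAP 9.1. The wording in SAP 9.1.1 about AE relationship and severity summaries could be stretched to all AEs, but it stands under the UADE heading, and Section 12.1 indexes no such table for AEs.

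What remains is that a listing is not a summary table. It leaves each reader to apply the once-per-subject, worst-grade rule by hand, and it does not present severity by event type.

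**Conclusion.** The point holds as a gap in reporting, not as a departure from protocol 7.7. Type is tabulated without severity or relationship, and those two are tabulated without type. The joint view exists in 2 of 5 tables, both for UADEs. All 12 anticipated events, 10 of them GI, fall outside that view unless an occurrence also meets the UADE definition. A serious but anticipated GI event could be absent from every by-term table because of the SAE exclusion.

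The consequence is limited: no efficacy estimate, test or sample size changes. What is affected is the study's ability to report in summary form which tolerability events were severe or attributed to the device, although GI severity is a stated protocol safety endpoint. It is a worthwhile and inexpensive improvement.

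The conclusion assumes that the table titles describe their content. That is reasonable here, because the UADE titles name severity or relationship where the table carries it. It also takes the SAE exclusion in SAP 9.1 literally.

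**What to change.** Add two safety-population tables to SAP 9.1 and 12.1, each covering all AEs, serious and non-serious:

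- AEs by system organ class, preferred term and maximum severity, with Standard of Care and RELiZORB columns.
- AEs by system organ class, preferred term and strongest relationship, limited to events starting on or after first RELiZORB use. A Standard of Care column does not suit this table, because causality is assessed against device use (protocol 6.2.1).

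Apply the counting rule already in SAP 9.1.1. Amend the sentence in 9.1 that excludes UADEs and SAEs from the AE summaries, since otherwise serious events would not reach the new tables. Reconcile 9.1 with 9.1.2 on whether SAEs are summarized.

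The cost is SAP wording and two extra tables, using severity and relationship fields that the overview already needs. No new data are collected.

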## 7.8 Efficacy Analysis

The measurement of the absorption of fats is an important efficacy endpoint, using absorption of fatty acids as surrogate biomarkers for fat absorption. LCPUFA plasma concentrations such as DHA and EPA will be an outcome variable, along with tissue accretion of LCPUFAs, measured as relative levels in erythrocyte membrane, and the profile of fatty acids in plasma. The fatty acid profile will also be used to calculate the ratio of omega-6 to omega-3 fatty acids, another outcome variable. Fat-soluble vitamin (A, D, and E) concentration is an additional efficacy endpoint and will be used as a laboratory outcome variable. Serum protein (total protein, prealbumin, albumin, and transferrin) concentrations and urinary leukotriene concentrations are additional endpoints and also represent laboratory outcome variables.

For all laboratory outcome variables, mean values from samples obtained on Day -14 and Day 0 will be compared using a two-sided test for comparison. The mean value from samples obtained on Day 0 will be used as the baseline for comparison with mean values from samples obtained on Days 30, 60, and 90 using ANOVA.

Body weight, height, and BMI are endpoints and clinical outcome variables. Absolute change in body weight from Day 0 through Days 30, 60, and 90 will be analyzed using ANOVA. To evaluate the effect of Relizorb use on weight and BMI, up to 4 weight and BMI recordings obtained from the medical record at 3 month intervals over the previous 12 months. The historical weight recordings will be used to calculate historical weight gain velocity, expressed as grams of body weight per kilogram of body weight per day. The study weight gain velocity will be similarly calculated by using the body weight values obtained on Days 0, 30, 60, and 90. The historical weight gain velocity will be compared to the study weight gain velocity using a two-sided test for comparison. In addition, the historical weight and BMI recordings, along with the weight and BMI values recorded on Day 0, will be used to calculate a standard score for weight and BMI values recorded on Days 30, 60, and 90.

Title: Absorption and Safety with Sustained Use of Relizorb™ Evaluation (Assure) Study in Patients With Cystic Fibrosis Receiving Enteral Feeding

## 8.0 STUDY COORDINATION AND MONITORING

## 8.1 Site Principal Investigators and Study Administrative Structure

The site PI will ensure that all persons assisting with the study are adequately qualified, informed about the protocol and any amendments to the protocol, the study treatments and their study-related duties and functions. The site PI must maintain a list of subinvestigators and other appropriately qualified and trained individuals to whom significant study-related duties have been delegated.

The site PI also certifies licensure to practice medicine in the state in which the study is conducted. Investigators are responsible for providing documentation of qualifications, GCP training, and current medical licensure and filing in a regulatory file.

